**7.1 End of Therapy & Follow-up**

STUDIES TO BE OBTAINED	End of Therapy
History	X
Physical Exam with VS	X
Ht, Wt, BSA	X
Performance Status	X
Pregnancy test*	X
CBC, differential, platelets	X
Urinalysis	X
Electrolytes including Ca ++ , PO 4 , Mg ++	X
Creatinine, SGPT, bilirubin	X
Total protein/albumin	X
Tumor Disease Evaluation	X

CEA and calcitonin (for patients with MTC only)	X
---	---

\*For female patients of childbearing potential.

Follow-up on this study is required at 30 days from the last date of protocol therapy, 6 months for the first year from the last date of protocol therapy and annually thereafter for up to five years from the date of study entry.

See COG Late Effects Guidelines for recommended post treatment follow-up:

<http://www-survivorshipguidelines.org/>

**Note:** Follow-up data are expected to be submitted per the Case Report Forms (CRFs).

## 7.2 Correlative Biology Studies

### 7.2.1 Pharmacokinetics

Pharmacokinetic (PK) studies will be **required** for the first 18 patients  $\geq 2$  to  $< 9$  years of age at enrollment and **optional** for all patients  $\geq 9$  to  $< 19$  years of age at enrollment at COG member sites.

Patients enrolled in mandatory PK studies must consent to PK collection and agree to provide all required PK samples.

#### 7.2.1.1 Sample Collection and Handling Instructions

Plasma samples will be collected for the purpose of determining concentrations of XL184 and/or metabolite concentrations for pharmacokinetic analysis.

#### Sampling Schedule and Collection

- Blood samples will be obtained at the following time points:
  - Cycle 1, Day 1: prior to dose; 2, 4, 8, and 20-28 hours after dose.
  - Cycle 1, Day 22 ( $\pm 2$  days): trough level prior to dose and 2-4 hours post dose. As patients may not be receiving the drug on all days of the week, care should be taken to draw PK on a day when drug is actually administered.
  - Cycle 2, Day 1: prior to dose
  - Cycle 3, Day 1: prior to dose
- For each time point, 3 mL of blood must be collected in a chilled K2-EDTA Vacutainer tubes (lavender top)
- For Cycle 1 Day 1 samples:
  - Record the exact time and date each sample is drawn and the time the drug is given.
- For Cycle 1 Day 22 samples:
  - Record the exact time and date each sample is drawn and the actual date and time the last dose of drug was administered prior to the collection of the trough sample.

#### Sample Processing and Labeling

- Tubes should be chilled on wet ice or in a refrigerator prior to collection. Immediately after blood collection, blood tubes should be inverted several times and then kept on wet ice until centrifuged. Within 30 minutes of blood

collection, samples should be separated by centrifugation for 10 minutes (1000 - 1200 g) at approximately 4°C. The resultant plasma should be withdrawn in approximately equal volumes into two (2) appropriately labeled polypropylene tubes for PK assay and stored (within 1 hour of the blood sampling time) at -70°C or lower until shipment. The analyst should attempt to transfer the maximum amount of plasma without disturbing the barrier between the red blood cells (bottom layer) and the plasma (top layer). One tube is the primary sample; the other tube is the back-up sample. Refer to PK Manual provided by Exelixis for additional sample processing instructions.

- Each tube must be labeled with the patient's COG I.D. and study number. (ADVL1622), and the date and time the sample was drawn. Data should be recorded on the Pharmacokinetic Study Form, which must accompany the sample(s).

#### **Sample Shipping Instructions**

- The primary samples collected for each subject should be shipped to Alturas Inc, on sufficient dry ice in an insulated container. Samples should be shipped between Monday and Wednesday for overnight delivery to ensure delivery to Alturas Analytics, Inc, before Friday. The back-up samples should be shipped to Alturas, Inc after confirmation of receipt of the primary samples.

#### **7.2.2 Pharmacodynamics**

For patients who provide consent, the effect of XL184 on immune cell subsets and immune gene signature will be analyzed by collecting blood samples at baseline (Cycle 1 Day 1, prior to 1st dose), Cycles 2 and 3 Day 1 pre-treatment.

##### **7.2.2.1 Sample Collection and Handling Instructions**

#### **Sampling Schedule and Collection**

- Blood samples will be obtained at the following time points:
  - Cycle 1, Day 1: prior to first dose
  - Cycle 2, Day 1: prior to dose
  - Cycle 3, Day 1: prior to dose
- For each time point, the following samples will be required:
  - 8 mL CPT citrate tube
  - 2.5 mL PAXgene blood RNA tube

### Sample Processing and Labeling

- Please notify the lab by email ([name]- [[contact]](mailto:[contact]); [name]- [[contact]](mailto:[contact]); [name]- [[contact]](mailto:[contact])) that the blood draw has been **scheduled**.
- Immediately after blood collection, blood tubes should be carefully inverted several times.
- Samples should be collected Monday through Thursday only, to arrive Tuesday through Friday. Do not ship to arrive on a government holiday. Samples may be shipped at room temp. A refrigerant gel pack such as the ThermoSafe Polar Pack PP24 Refrigerant Gel Pack should be included.
- Each tube must be labeled with the patient's COG I.D. and study number (ADVL1622), and the date and time the sample was drawn. Data should be recorded on the Pharmacodynamic Study Form, which must accompany the sample(s).

### Sample Shipping Instructions

Notify the lab when the sample is being shipped, including in the email the FedEx tracking number. Send samples by **FedEx Priority Overnight** Shipping. The NIH is not open on weekends or government holidays. Be careful not to ship any samples to arrive on a Saturday, Sunday or government holiday. If you are not certain whether the government will be open please send an email to the addresses below at any time and we will respond as quickly as possible.

#### 7.2.3 Tissue Banking Study

Submission of tumor tissue to be banked for future research studies is strongly encouraged. Tumor tissue obtained as a result of biopsy or resection at initial diagnosis, and/or of a suspected disease recurrence site prior to therapy, and/or of a suspected disease recurrence during the first 12 months from the time of enrollment is requested for banking. Snap frozen, formalin-fixed and paraffin-embedded (FFPE) blocks or unstained slides (at least 10 cut sequentially from the same block) will be accepted.

COG sites: if a block or unstained slides have been submitted already on APEC14B1 (Project:EveryChild), additional tissue is not required.

### Sample Labeling and Shipping

Label biology specimens with:

- the patient's COG ID number
- specimen type (primary or metastatic)
- collection date

Include the surgical pathology ID (SPID) number and block number in the labeling when submitting a block or slides.

### Include a transmittal form, pathology report and operative report with each shipment.

The Biopathology Center (BPC) will provide a specimen procurement kit for shipping frozen tumor tissue to the BPC. Kits are provided to sites in the US and Canada only.

COG sites: Kits are ordered via the BPC Kit Management application. To access the application click on the 'Biopathology Center Application' link on either the Protocol or the CRA Home Page of the COG web site. On the Biopathology Center Applications page, select the BPC Kit Management link to enter the Kit Management application.

Non-COG Sites: Sites can order kits online via the Kit Management link <http://ricapps.nationwidechildrens.org/BPCKitManagement/>.

- Snap frozen tissue must be sent on dry ice. Using at least 4 lbs. total, layer dry ice in the bottom of the kit until it is approximately one third full. Place the frozen specimens on top of the dry ice. Cover the specimens with dry ice until the compartment is almost completely full. Secure the foam lid. Remember to include the COG Specimen Transmittal Form, pathology report and operative report with each shipment. Close the outer lid of the kit and tape with filament or other durable packing tape.
- Attach a label to the top of the kit. COG sites will access the Kit Management application to print a FedEx shipping label. Non-COG sites should contact the BPC by [contact]) or email ([[contact]](mailto:[contact])) to request a shipping label. A blank label is provided in the kit to use when printing the shipping label. **A shipping label will only be provided when frozen tissue is submitted.** Blocks and slides must be shipped using the institution's courier account or regular mail. Complete the dry ice label (UN 1845) and secure both this label and the Exempt Human Specimen label to the side of the box.

### 7.3 Central Review

The pertinent imaging studies (CT, MR, etc.) of those patients who respond to therapy or have long term stable disease on protocol therapy will be centrally reviewed. COG Operations Center will notify the Imaging Research Center of any patient requiring central review. The Imaging Research Center will then request that the treating institution forward the pertinent images for central review. The central image evaluation results will be entered into Rave for review and for data analysis.

Long term stable disease for central review is defined as having at least 6 consecutive cycles of stable disease for the non-osteosarcoma strata and at least 4 consecutive cycles for the osteosarcoma stratum.

The images are to be forwarded electronically to the Imaging Research Center at Children's Hospital Los Angeles via the ImageInBox.

Institutions that are not connected via the ImageInBox can send the images on hard copy film, CD ROM, DVD, USB flash drive or by FTP. Submitted imaging studies should be clearly marked with the COG patient ID, study number (ADVL1622) and date, and shipped to [name] at the address below:

[name], CCRP  
Administrator, Imaging Research Center  
Children's Hospital Los Angeles  
[name]  
[name]  
[contact]  
[contact]  
Email: [[contact]](mailto:[contact])

## 8.0 CRITERIA FOR REMOVAL FROM PROTOCOL THERAPY AND OFF STUDY CRITERIA

### 8.1 Criteria for Removal From Protocol Therapy

- a) Progressive disease.
- b) Adverse Events requiring removal from protocol therapy, as stated in [Section 5.0](#).
- c) Patients who receive concurrent anticancer or investigational therapy, as stated in [Section 4.1.4](#).
- d) Refusal of further protocol therapy by patient/parent/guardian.
- e) Physician determines it is in patient's best interest.
- f) Repeat eligibility studies (if required) are outside the parameters required for eligibility.
- g) Non-compliance that in the opinion of the investigator does not allow for ongoing participation.
- h) Patients who develop a second malignant neoplasm.

- i) Pregnancy.
- j) Study is terminated by sponsor.

Patients who are removed from protocol therapy (except for 8.1.f) are to be followed until they meet the criteria for Off Study (see below). Follow-up data will be required unless consent was withdrawn.

## 8.2 Off Study Criteria

- a) Death.
- b) Lost to follow-up.
- c) Entry into another COG study with tumor therapeutic intent (e.g., at recurrence).
- d) Patient does not receive protocol treatment after study enrollment.
- d) Withdrawal of consent for any further data submission.
- e) The fifth anniversary of the date the patient was enrolled on this study.

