### 1.2 Secondary Aims

1.2.1 To further define XL184 related toxicities in pediatric, adolescent and young adult patients.

1.2.2 To further define XL184 pharmacokinetics in the pediatric and adolescent patients.

1.2.3 To estimate 1-year time to progression, progression free survival (PFS) and overall survival for each stratum, and if feasible to compare to historical controls.

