## 3.2 Eligibility: Inclusion Criteria

**Important note: The inclusion criteria listed below are interpreted literally and cannot be waived. All clinical and laboratory data required for determining eligibility of a patient enrolled on this trial must be available in the patient's medical/research record. These source documents must be available for verification at the time of audit.**

**All clinical and laboratory studies to determine eligibility must be performed within 7 days prior to enrollment unless otherwise indicated. Laboratory values used to assess eligibility must be no older than seven (7) days at the start of therapy. Laboratory tests need not be repeated if therapy starts within seven (7) days of obtaining labs to assess eligibility. If a post-enrollment lab value is outside the limits of eligibility, or laboratory values are > 7 days old, then the following laboratory evaluations must be re-checked within 48 hours prior to initiating therapy: CBC with differential, bilirubin, ALT (SGPT) and serum creatinine. If the recheck is outside the limits of eligibility, the patient may not receive protocol therapy and will be considered off protocol therapy. Imaging studies, bone marrow biopsy and/or aspirate, if applicable, must be obtained within 2 weeks prior to start of protocol therapy (repeat the tumor imaging if necessary).**

3.2.1 Age: Patients must be  $\geq 2$  and  $\leq 30$  years of age at the time of study entry for all strata except upper age limit of  $\leq 18$  years of age for MTC, RCC and HCC.

3.2.2 Body Surface Area (BSA): Patients must have a body surface area  $\geq 0.35$  m^2.

3.2.3 Diagnosis: Patients must have recurrent or refractory disease, or newly diagnosed disease with no known curative therapy or therapy proven to prolong survival with an acceptable quality of life. Patients must have had histologic verification of one of the malignancies listed below at original diagnosis or at relapse.

- Ewing sarcoma
- Rhabdomyosarcoma (RMS)
- Non-rhabdomyosarcoma soft tissue sarcomas (STS) including microphthalmia transcription factor associated STS (alveolar soft part sarcoma (ASPS) and clear cell sarcoma (CCS))
- Osteosarcoma
- Wilms tumor
- Rare tumors
  - Medullary thyroid carcinoma (MTC)

- Renal cell carcinoma (RCC)
- Hepatocellular carcinoma (HCC)
- Hepatoblastoma
- Adrenocortical carcinoma

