### 9.3 Methods of Analysis

Toxicity tables will be constructed to summarize the observed incidence by type of toxicity and grade. A patient will be counted only once for a given toxicity for the worst grade of that toxicity reported for that patient. Toxicity information recorded will include the type, severity, time of onset, time of resolution, and the probable association with the study regimen.

Time-to-event analyses (time to progression, progression-free survival, and overall survival) will be computed when all patients in a stratum have at least one year of follow-up.

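### Follow-up stops when a patient enters another COG therapeutic study, so the one-year overall survival estimates are exposed to dependent censoring of unknown direction

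*Combined protocol and SAP*

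**What the plan says.** Section 1.2.3 sets the secondary aim: "To estimate 1-year time to progression, progression free survival (PFS) and overall survival for each stratum, and if feasible to compare to historical controls". Section 9.3 says that the time-to-event analyses "will be computed when all patients in a stratum have at least one year of follow-up". Section 7.1 schedules visits at 30 days and 6 months after the end of therapy, and then "annually thereafter for up to five years from the date of study entry".

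Sections 8.1 and 8.2 decide how long a patient is actually followed. Patients taken off protocol therapy "are to be followed until they meet the criteria for Off Study (see below). Follow-up data will be required unless consent was withdrawn". The off-study list in Section 8.2 includes death, loss to follow-up, withdrawal of consent, "The fifth anniversary of the date the patient was enrolled on this study" and, as item (c), "Entry into another COG study with tumor therapeutic intent (e.g., at recurrence".

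The documents give no definition of OS, no censoring rule for it, no survival-only follow-up after item (c), no link to data from the later COG study, and no sensitivity analysis for patients who leave this way.

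**The concern.** Kaplan-Meier estimation of OS assumes that a patient censored at a given time has the same outlook as those still at risk. Item (c) makes that doubtful. Its own example is recurrence, and the trial population is one in which further trials are likely to be sought: "Patients must have recurrent or refractory disease, or newly diagnosed disease with no known curative therapy". Those who leave have usually progressed, which marks a worse outlook than that of patients still progression-free. They are also alive and fit enough to be eligible elsewhere, which marks a better outlook than that of other progressed patients. Either feature links the censoring time to prognosis.

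At stake is a named secondary estimate, reported per stratum and possibly set against historical controls. Outcomes that were not collected cannot be recovered at analysis without untestable assumptions. There is also a tension in the text: Section 9.3 asks for a year of follow-up on everyone in the stratum, while Section 8.2(c) can end follow-up before that.

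**Working it through.** The documents state no event count, precision target or dropout rate for OS, so there is no plan figure to reproduce.

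**Step 1. Does follow-up really end?** Section 8.1 follows patients up to an off-study criterion, and Section 8.2(c) is one. The sentence in Section 8.1 requiring follow-up data unless consent is withdrawn governs the period up to that point and does not extend it. The five-year schedule in Section 7.1 is cut short in the same way.

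**Step 2. How often would a stratum contain such a patient?** Let q be the assumed probability that a patient leaves alive under 8.2(c) within 12 months. The chance of at least one in a stratum of n is 1 - (1 - q)^n. For q = 5% and n = 20 this is 1 - 0.95^20 = 64%. Stratum sizes are from Section 9.2: 13 then 20, and 29 for osteosarcoma at full accrual.

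| q (assumed) | n = 13 | n = 20 | n = 29 |
|---|---|---|---|
| 2% | 23% | 33% | 44% |
| 5% | 49% | 64% | 77% |
| 10% | 75% | 88% | 95% |
| 20% | 94.5% | 98.8% | 99.8% |

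**Step 3. What does the censoring do to one-year OS?** Every input here is an assumption.
- Time to progression is exponential with median 2 or 4 months. Death occurs only after progression.
- Half the patients are fitter, with median post-progression survival of 8 months. The other half have a median of 8, 4 or 2 months.
- 10%, 30% or 50% of all patients are selected to enter another COG study one month after progression, if still alive. They come either from the fitter half only or from both halves equally.
- OS is censored at entry. The 12-month Kaplan-Meier estimate is compared with true 12-month survival, with 400,000 simulated patients per scenario.

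Bias in percentage points (estimate minus truth), shown for 10% / 30% / 50% selected:

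| Median time to progression | Median post-progression survival, less fit half | Fitter patients only enter | Entry unrelated to fitness |
|---|---|---|---|
| 2 months | 8 months | +0.5 / +1.8 / +3.5 | +0.5 / +1.7 / +3.7 |
| 2 months | 4 months | -0.5 / -2.1 / -5.1 | +0.6 / +2.1 / +4.2 |
| 2 months | 2 months | -1.1 / -4.4 / -11.4 | +0.6 / +2.0 / +4.0 |
| 4 months | 8 months | +1.1 / +3.6 / +7.2 | +1.0 / +3.6 / +7.1 |
| 4 months | 4 months | +0.4 / +1.3 / +2.4 | +1.2 / +4.3 / +8.3 |
| 4 months | 2 months | 0.0 / -0.2 / -0.6 | +1.3 / +4.4 / +8.5 |

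Where the two halves do not differ (8 months each), the two entry rules are the same and the columns agree to within simulation error. When entry is unrelated to fitness the bias is upward: only progressed patients are removed, so those left at risk are weighted towards the progression-free. When only the fitter patients leave, the remaining progressed patients are the sicker ones, which pulls the estimate down; the net sign depends on which effect is larger.

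**Step 4. Which other endpoints are touched?** Progression is the first reason for removal in Section 8.1, so the event for progression-free survival and time to progression normally comes before item (c). The exception is a patient who stops for toxicity, refusal or physician decision and joins another COG study before progressing. The decision rules in Section 9.2 use response and four-month disease control, not OS.

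**The case against.** A reader might infer that OS is biased downward, because patients well enough for another trial are censored. A simple model appears to confirm it. Suppose those who stay have a median OS of 8 months (hazard ln 2/8 per month), and a fraction f with hazard ratio h all leave at month 3. With f = 0.4 and h = 0.4:
- True one-year OS is 0.6 × exp(-12 ln 2/8) + 0.4 × exp(-0.4 × 12 ln 2/8) = 0.476.
- Kaplan-Meier gives S(3) × exp(-9 ln 2/8) = 0.823 × 0.458 = 0.377, a shortfall of 9.9 points.

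That model fixes the sign by giving leavers the lower hazard from the start, and it ignores the tie to progression that the rule itself suggests. Its size is equally a product of its inputs: spreading the exits evenly over months 3 to 12 gives 4.3 points, and f = 0.1 with h = 0.7 gives 1.0 point even with exit at month 3. Step 3 yields either sign. The documents support no direction and no range.

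A reader might also infer that the one-year follow-up cannot be completed at all. That is too broad. Item (c) covers only COG studies with therapeutic intent, so non-COG trials, commercial drugs and supportive care do not trigger it. Patients who die in the first year do not accrue twelve months either, so Section 9.3 can sensibly be read as potential follow-up, one year after the last enrollment. On that reading item (c) does not delay the analysis. What stands is that the wording should say so.

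Two further points are fair. The OS censoring date is inferred from Sections 8.1 and 8.2; the plan does not state it. And strata are small: at one-year OS of 0.40, the 95% half-width is 1.96 × sqrt(0.4 × 0.6/20) = 21 points for n = 20 and 18 points for n = 29, before any censoring, so sampling error will often exceed the bias. That limits the practical weight of the point. It does not remove the defect, because a wide interval does not show a bias and a comparison with historical controls would carry it.

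**Conclusion.** The concern holds in this form. Sections 8.1 and 8.2(c) together end follow-up at entry to another COG therapeutic study, which exposes the one-year OS estimate in each stratum to censoring linked to prognosis. Direction and size cannot be settled from the documents. Under the assumptions of Step 3 the bias is within about 1 point at 10% selected, within about 4 points at 30%, and between -11 and +9 points at 50%. These figures illustrate sensitivity and are not predictions.

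The effect on progression-free survival and time to progression is confined to patients who enter another COG study before progression, whose number is not given. No primary conclusion changes. The conflict with Section 9.3 is literal and concerns only patients who leave alive within a year.

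The point is worth acting on because following the plan as written loses the data, and the repair is inexpensive.

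**What to change.** 1. Amend Section 8.2(c) so that a patient who enters another COG therapeutic study stays in follow-up for vital status, and for first progression if none has been recorded, until the fifth anniversary of enrollment. Use linkage through the COG patient ID where possible; Section 3.1.1 already carries that number across a patient's later dealings with the group.
2. State in Section 9.3 that OS is not censored at entry to another study.
3. Restate the Section 9.3 trigger as one year after the last enrollment in the stratum.

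The cost is a wording amendment and a small amount of additional vital-status collection for the patients concerned. Sample size, the two-stage rules and the primary analyses stay as they are.
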